## **5.10 Quality control/monitoring**

The study will be monitored according to ICH/GCP by visits and calls to the investigator. During site visits, the monitor shall review original patient records and document retention. Additionally, the monitor shall observe study procedure and will discuss any problem with the

investigator. The investigator will provide direct access to source data/documents for trial related monitoring audits, EC review and regulatory inspections.

Monitoring will be provided by Clinical trial Unit at the Oncology Department at Sahlgrenska University Hospital.

### **5.11 Records retention/subject identification**

It is the investigator's responsibility to retain sufficient information regarding the identity of the patients, so that any Health Authorities may access this information, if needed. Copies of all pertinent information, including patient identity and allocation number and individual patient data records, will be retained in a confidential manner by the investigator for a minimum period of 15 years from study completion.

### **5.12 Data management**

Data collection during the study will be performed by the monitor and data management will be performed at Study coordinating center.

### **5.13 Ethics**

The study will start after approval from authority and Ethical committee and it is the responsibility of the Investigator-Sponsor to supply the co-investigators with a copy of the final assessment. This study will be conducted in compliance with the protocol and in accordance with the ethical principles put forward in the Declaration of Helsinki and in accordance with GCP rules.

The rights, safety and well-being of the trial subjects are the most important considerations and should prevail over interests of science and society.

Study personnel involved in conducting this trial will be qualified by education, training and experience to perform their respective tasks.

## **6.0 Study Population**

### **6.1 Source**

Patients with histologically confirmed thymoma or thymic carcinoma

## **6.2 Inclusion Criteria**

- Histological or cytological diagnosis of thymoma or thymic carcinoma
- With radical surgery stage III, IVa and selected stage II with type B2, B3 or thymic carcinoma according to local routine
- With non-radical surgery (R1 or R2), stage I - IVa, any histology
- Medically inoperable, or patient refusing surgery, stage I - IVa, any histology
- PS WHO 0 - 2.
- $FEV_1 \geq 1L$  or  $\geq 40\%$  of predicted and CO diffusion capacity  $> 40\%$  of predicted (post-operative measures).
- Age  $\geq 18$  years, no upper age limit.
- Written informed consent from patients.

## **6.3 Exclusion Criteria**

- Masaoka-Koga stage IVb (distant metastases)
- Pregnancy.
- Serious concomitant systemic disorder incompatible with the study.
- Tumour motion  $> 0.5$  cm on two repeated 4DCT

## **7.0 Evaluations**

### **7.1 Pre-study evaluations**

- CT scan thorax and upper abdomen including adrenals, not older than 4 week, documentation of measurable and unmeasurable disease sites.
- Medical history
- Physical examination
- Performance status according to WHO
- Assessment of quality of life according to QLQ 30+LC14

- Pre-treatment weight loss registration
- Electrocardiogram (ECG)
- Transthoracic echocardiogram (TTE)/UCG
- Spirometry with CO diffusion capacity
- Body weight and length
- Assessment of symptoms at baseline according to NCI-CTCAE criteria, version 4.0
- Pregnancy Test

All women of childbearing potential must have a negative serum or urine pregnancy test (minimum sensitivity 25 IU/L of  $\beta$ -HCG) within 72 hours prior to the start of study.

- Haematology: Haemoglobin, WBCC, Neutrophils and Platelets count.
- Chemistry: Serum creatinine, calcium and albumin, Bilirubin, Alkaline Phosphates, LDH, ASAT, ALAT, CRP, TNT, NT-proBNP

## **7.2 On Treatment evaluation**

- Recording of toxicity and performance status, at week 1, 3 and 5 during treatment
- Weight every week
- Registration of volumes for GTV, PTV, constraints doses to normal tissues: Lung:  $V_5$ ,  $V_{20}$ ,  $V_{40}$ , MLD. Esophagus:  $D_{2\%}$ , mean dose. Heart: mean dose,  $V_{40}$ . LADCA:  $D_{2\%}$ , mean dose Spinal cord:  $D_{2\%}$

## **7.3 Post Treatment evaluation/Follow up**

First follow-up 4 weeks after completion of therapy, then at four months and every three months thereafter during the first year. After that follow-up every six months until end of study

- Recording of persistent or new toxicity
- Performance status
- Weight
- Tumour response evaluation with CT scan at 4, 7 and 13 months after therapy and every 6 months thereafter or if clinically indicated. Chest x-ray is sufficient at other follow-up visits.

- Quality of life according to QLQ30+LC14 at baseline, week 3 during treatment, end of treatment, 1, 3, 6 and 12 months after completion of radiotherapy. Thereafter at 2, 3 and 5 years after treatment.
- Spirometry with CO diffusion capacity at 6 months after therapy and at end of study

#### 7.4 Transthoracic echocardiogram (TTE)/UCG

A comprehensive TTE examination will be performed at three times: within two weeks prior to radiation therapy, within two weeks from completion of radiation therapy and at the end of the study. The TTE examinations are performed using the existing equipment at the local hospital. Age, gender, length and weight of the patient are recorded before start. During examination heart rate and presence of arrhythmias are documented. Image sampling follows a standardised protocol (Appendix) and is performed by a biomedical scientist or cardiologist at the local hospital. The examination is thereafter transferred (by CD/DVD) for central evaluation by study responsible cardiologist. All values are related to the age, gender and body size of the patient.

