**11.0 Statistics**

**12.0 Publication**

**13.0 References**

**14.0 Appendix**

14.1 Prothym – transthoracic echocardiogram (TTE) protocol

14.2 Performance status

14.3 CTC version 4.0

14.4 Masaoka-Koga staging system

14.5 WHO classification system of thymoma

## 1.0 Synopsis

Title of study	PROTHYM Trial  Proton radiotherapy of thymic malignancies  The study is supported by SLUSG, Swedish Lung Cancer Study Group
Principal investigator	[name] MD PhD
Co-investigators	[name] MD [name] Med Phys. PhD [name] MD [name] MD [name] [name] [name] [name] [name] MD [name] [name] [name] MD [name] [name] [name] MD [name], PhD
Study centres	Skandion Clinic, Uppsala, Sahlgrenska University Hospital, Gothenburg, Karolinska University Hospital, Stockholm, Akademiska Hospital, Uppsala, Norrlands University Hospital, Umeå, Örebro University Hospital, Linköping University Hospital, Skåne University Hospital, Lund
Study phase	Prospective, non-randomized phase II study
Number of patients	40 patients
Study Start	Sep 2017
Planned study period	Recruitment Start Date : Sep/2017 Target recruitment period:60 months Sep/2022) Follow up period. End date: 5 years from last treatment.
Study objectives	Primary : Toxicity (e.g. cardiac and pulmonary toxicity) and Local control at 5 year Secondary : PFS

	
Overall survival
 
Quality of life, measured by EORTC QLQ 30 + LC 14
 
Relapse pattern

Study design and plan	
This is a multicentre non-randomized phase II study of proton beam radiotherapy in patients with thymic epithelial tumours (i.e. thymoma and thymic carcinoma) in the post-operative setting or in inoperable patients with localized disease.
 
Patients not willing or for any reason unsuitable to undergo proton treatment will be asked to participate in a follow-up assessment after the regular photon treatment in the same manner as the included patients.

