Radiotherapy with photons for TET patients has been reported feasible and with acceptable toxicity. Treatment is generally given with IMRT-technique and doses in the literature varies between 45 and 60 Gy with 1.8 or 2 Gy/fraction.

Many of the thymoma patients will become long time survivors and thus may suffer from late toxicities such as radiation induced lung disease (RILD) (11) or radiation induced heart disease (RIHD) (12-13). For many years RIHD has been of major concern when irradiating patients with left-sided breast cancer and Hodgkin's disease. It is considered a late side effect which may become manifest 5-10 years after completion of radiotherapy, although earlier onset may occur. It includes a wide range of symptoms such as pericarditis, myocardial infarction, valvular heart disease and coronary heart disease (14-15). Lately this has become a greater concern when treating thoracic malignancies such as lung and esophageal cancer (16). Depending on the good prognosis, there is a strong rationale as to try to limit the cardiac dose to the thymoma patients. Comparing treatment plans for protons vs photons has shown that it is possible to reduce the cardiac dose with protons (personal communication [name] & [name]).

How to detect and follow-up on RIHD is an ongoing subject for discussion. Different imaging techniques have been suggested (17-18) and there is also some data on biomarkers predicting cardiac toxicity after chemotherapy and radiation therapy (19). There is, however, no golden standard regarding screening for RIHD.

Radiotherapy with protons have emerged as a potential possibility to achieve local control and eventually reduce the risk for late toxicity and secondary tumors. From early on, thymic malignancies was recognized as a group who would eventually benefit from proton therapy (20-21). Treating thoracic malignancies with protons is cumbersome because of many reasons; tumor and organs at risk motion may result in interplay effects which compromise dose distribution being one of them. Movement of mediastinal structures occurs but seems to

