#### **4.1.1 Primary Objective**

Toxicity (eg cardiac and pulmonary toxicity).

Local control at 5 years. Local control is defined as freedom of locally progressive disease; ie CR (complete remission) or SD (stable disease) based on CT or PET/CT evaluation

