## **5.0 Study Design**

### **5.1 Description**

This is an open, non-randomized multicentre, phase II trial, to investigate the efficacy and toxicity in PBS proton therapy of thymic malignancies

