## **11.0 Statistics**

We will perform a Kaplan-Meier analysis with the aim to compare our data with published historic data from the ITMIG international database and other datasets. Since there is a limited amount of published thymoma data concerning heart we will also try to relate heart toxicity with published data from Hodgkin and breast cancer studies. Toxicity data will be analysed descriptively and there will be a comparison between the proton patients and photon control group. 40 patients will be included in the study

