## **14.0 Appendix**

### **Appendix 14.1**

#### **PROTHYM - TRANSTHORACIC ECHOCARDIOGRAM (TTE) PROTOCOL**

Image sampling is performed by a biomedical scientist or cardiologist at the local hospital. The examination is thereafter transferred (by CD/DVD) for evaluation by study responsible cardiologist.

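### The protocol sends all echocardiograms to one central study cardiologist in an open trial but makes no provision to mask that reader to proton or photon treatment

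*Protocol*

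**What the plan says.** Section 5.1 describes the design: "This is an open, non-randomized multicentre, phase II trial". Section 4.1.1 opens the primary objective with "Toxicity (eg cardiac and pulmonary toxicity", next to local control at 5 years. Section 11.0 states: "Toxicity data will be analysed descriptively and there will be a comparison between the proton patients and photon control group". The Synopsis asks patients who do not receive protons to take part in a "follow-up assessment after the regular photon treatment in the same manner as the included patients", so photon patients should have the same echocardiograms.

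Section 7.4 places these examinations before radiotherapy, shortly after it and at the end of the study. Images are taken locally to a standard protocol. Then "The examination is thereafter transferred (by CD/DVD) for central evaluation by study responsible cardiologist". Appendix 14.1 says the same: "The examination is thereafter transferred (by CD/DVD) for evaluation by study responsible cardiologist". Neither place mentions coding the discs, removing treatment information or masking the reader, and no other section does.

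Section 3.0 states the expected direction of effect: "Comparing treatment plans for protons vs photons has shown that it is possible to reduce the cardiac dose with protons". Section 12.0 plans a separate publication of the cardiological data.

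**The concern.** All the conditions for reader bias are present. Treatment is open, the reader belongs to the study, the protocol states an expectation in favour of protons, and the readings can feed a comparison of the two modalities. Several items in Appendix 14.1 rest on tracing or visual judgement: ventricular volumes and wall motion, colour Doppler of the valves, the E/A and S/D measures, and the variation of the vena cava. A reader who knows the modality could, without intending to, read one group more favourably than the other.

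The analysis cannot separate such a shift from a true effect, because it coincides with the treatment groups. Only a masked re-reading of the stored images would remove it. The files already pass through a central step, so the safeguard is available at little cost before reading.

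**Working it through.** The protocol has no figure to reproduce. It gives 40 patients without alpha, power, effect size or SD, and no size for the photon group. The check is therefore a reading of the text, followed by an illustration.

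**Step 1. Does the protocol secure masking to modality?** Section 7.4 and Appendix 14.1 set out the whole chain: local acquisition, transfer on disc, evaluation by the study cardiologist. Appendix 14.1 lists age, gender, length, weight, heart rate and arrhythmias to be noted. Modality is not on that list, but nothing says it must be withheld or that identity must be removed. Masking is not secured.

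**Step 2. Which kind of knowledge biases the group difference?** Write a patient's recorded change from baseline as

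recorded change = true change + t + b × (1 if proton, 0 if photon),

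where t is a shift from knowing the time point and b a shift from knowing the modality. Subtracting the photon mean from the proton mean gives

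recorded difference = true group difference (including any confounding) + b.

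The term t cancels if it is the same in both groups. Only b enters the comparison, and it enters one for one. Masking to modality sets b to zero and leaves the confounding as it was.

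**Step 3. How large could b be against sampling error?** Assumed inputs, none of them in the documents: m = 10, 20 or 40 photon patients; b = 0.25 or 0.5 SD of the echo measure; equal SD in both groups; no true difference and no confounding. From the protocol: 40 patients, taken as the proton group.

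- SE in SD units = √(1/40 + 1/m)
- Shift in standard errors: d = b / SE
- Chance of a nominal two-sided 5% difference = Φ(d − 1.96) + Φ(−d − 1.96)

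| m | SE | b = 0.25: d | chance | b = 0.5: d | chance |
|---|---|---|---|---|---|
| 10 | 0.354 | 0.71 | 10.9% | 1.41 | 29.3% |
| 20 | 0.274 | 0.91 | 15.0% | 1.83 | 44.7% |
| 40 | 0.224 | 1.12 | 20.1% | 2.24 | 60.9% |

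With b = 0 the chance is 5.0% in every row. Because section 11.0 plans a descriptive analysis with no stated test, the columns for d matter more. They show an assumed shift comparable to, or larger than, the sampling error of the difference. The percentages are only a yardstick.

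**The case against.** The strongest reply is that the protocol is silent and does not describe an unmasked reading. A reader might infer that the cardiologist is known to see the modality. The documents do not support that: modality is not among the items to be noted, and the examinations come from the local hospital, not the proton clinic, so the sender need not reveal the treatment. Section 8.0 also refers to a protocol for the photon cohort, which may be a separate document and is not at hand. What remains is that masking is left to chance in an open trial whose reading procedure is otherwise written out. How images are handled before reading is trial conduct and belongs in that procedure.

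A reader might also infer that the echocardiogram is the primary endpoint. No echo variable is named as such. Investigators grade toxicity with CTCAE 4.0 (section 9.2), and ECG, NT-proBNP and troponin T also inform cardiac toxicity. Echocardiography is one component.

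Third, the gain is limited. Photon patients include those unwilling or unsuitable for protons, those with tumour motion above 0.5 cm (section 8.6) and those whose photon plan is superior (section 8.0), treated according to local practice (section 5.3). Masking does not touch this confounding, nor any influence from unmasked local acquisition. This stands. Still, reader bias is a separate error that recorded covariates cannot adjust for, and it is the part that can be avoided.

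Finally, one might want the reader masked to time point as well, with each patient's examinations read in random order. That would hold the earlier examinations until the one at 5 years and keep them from the safety analysis after 15 subjects (section 10.2). The protocol describes no separate local clinical reading to fill the gap. As Step 2 shows, a time-point shift common to both groups cancels in the comparison, so the proton-photon difference does not need this.

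**Conclusion.** The point holds in limited form. The protocol makes no provision to mask the central echo reader to modality, in an open trial with a stated expectation and a planned comparison of the two modalities. Reader expectation could therefore bias the proton-photon difference in the judgement-dependent echo measures.

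The documents give no figure for this bias, and none can be derived from them. The range of about 0.7 to 2.2 standard errors rests wholly on assumed shifts of 0.25 to 0.5 SD and 10 to 40 photon patients. It shows what such a shift would do, not that one exists. The false-positive percentages might be read as an inflated type I error of this trial. That does not follow, because no test or significance level is specified for toxicity.

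This is a worthwhile, inexpensive improvement to the conduct of the trial. It does not invalidate the cardiac results, and it would not turn the comparison with a non-randomized photon group into an unconfounded one.

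**What to change.** Amend section 7.4 and Appendix 14.1 to state that:

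- before a disc goes to the study cardiologist, the Clinical Trial Unit replaces patient identity with a study code and removes any reference to proton or photon treatment;
- age, gender, length and weight stay with the examination, since the values are related to them;
- the cardiologist records and locks the values for each examination without access to modality.

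Readings are still made on arrival, so they remain available for the safety analysis after 15 subjects. The trial unit holds the key and can link a coded result back to the patient whenever needed.

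The cost is protocol wording and a small coding step at a unit that already registers patients (section 5.9) and handles the questionnaires centrally (section 5.6). It needs no additional reader, examination or reading. Where examinations have already been read, stored images could be re-read under the same masking.

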#### 7.5 Schedule of assessments

Table 1

	Prior to RT	During RT	End of RT	Within 2 weeks from RT	4 weeks
Medical history	X				
Physical examination	X	X	X		X
Weight & PS	X	X	X		X
NT-Pro-BNP, TNT, CRP	X	X	X		X
Hematology	X		X		X
Creatinine, calcium, albumin, bilirubin, ALP, ASAT, ALAT, LDH	X		X		X
Electrocardiogram	X	X	X	X	X
PET-CT-scan	optional				
Tumor assessment by CT 	X				
TTE/UCG	X			X	

Spirometry 	X				
Assessment symptoms and toxicity	X	X	X		X
QLQ 	X		X		

	4 months from RT	6 months from RT	Follow up	End of study	
Medical history					
Physical examination	X		X	X	
Weight & PS	X		X	X	
NT-Pro-BNP, TNT, CRP	X		X	X	
Hematology	X		optional		
Creatinine, calcium, albumin, bilirubin, ALP, ASAT, ALAT, LDH	X		optional		
Electrocardiogram	X		X	X	
PET-CT-scan	optional				
Tumor assessment by CT 	X		X	X	
TTE/UCG	X			X	
Spirometry 		X		X	
Assessment symptoms and toxicity	X		X	X	
QLQ 	X	X	X	X	

1. CT scan will be performed before inclusion (not older than 4 weeks), at 4, 7, 10 and 13 months after therapy and every 6 months thereafter during follow up or until progressive disease.
2. Quality of life will be measured by using QLQ C30 and LC14 module at baseline, week 3 of treatment, end of treatment ,1, 3, 6 and 12 months after completion of therapy. Thereafter at 2, 3 and 5 years after treatment.
3. Spirometry including CO diffusion capacity will be performed before inclusion, after 6 months and at end of study

## 8.0 Radiotherapy

All patients included in the study must be able to receive prescribed dose to the target volume without exceeding absorbed doses to the organs at risk. Dose planning shall be performed with a CT-based system. A 4DCT for the planning is mandatory and has to be repeated before start of treatment. If tumour motion exceeds 0.5 cm proton therapy will not be given. All patients needs to have a photon backup plan, preferably with IMRT/VMAT technique although 3DCRT is allowed. Treatment planning can be performed on either average CT from the 4D-CT or a regular CT. Slice thickness is to be maximally 3 mm. If the photon plan is superior to the proton plan, the photon plan is to be used and the patient will be excluded from the study and followed up according to the photon cohort protocol.

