## **4.0 Rationale and Objective of the study**

### **4.1 Objective**

To explore whether proton radiotherapy is feasible and results in an acceptable local control

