## **5.9 Patient registration**

Before patients agree to participate in this trial all patients will be given oral and written information. A "Patient information sheet" and a consent form, prepared in the local language will be handed out to the patients. The formal consent form must be signed and dated by the patients and investigator before they are submitted to any study-specific procedure.

Patients that fulfil the eligibility criteria and have signed and dated the formal consent will be registered by phone to the Clinical Trial Unit, Sahlgrenska University Hospital, Göteborg at [contact]. Treatment should start within four weeks from registration.

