## **8.6 Patient monitoring before and during treatment**

Before treatment starts patients will undergo a control 4D-CT at Skandion Clinic. If tumour motion exceeds 0.5 cm proton treatment will not be given and patient will receive the photon backup plan instead.

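### Section 8.0 excludes patients whose photon plan is superior, by an undefined and unlisted criterion, and on the natural reading pools them with refusers in the photon comparator

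*Protocol*

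**What the plan says.** The overall objective in Section 4.1 is "To explore whether proton radiotherapy is feasible and results in an acceptable local control". Section 4.1.1 makes toxicity a primary objective alongside local control at 5 years.

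Section 8.0 requires a photon backup plan for everyone. If that plan is superior it is used, and "the patient will be excluded from the study and followed up according to the photon cohort protocol". Section 8.1 adds that such patients receive fractionation and dose by local routine.

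On entry, Section 5.9 states: "Patients that fulfil the eligibility criteria and have signed and dated the formal consent will be registered by phone". Section 6.3 lists four exclusions: stage IVb, pregnancy, serious concomitant disorder, and tumour motion above 0.5 cm on repeated 4DCT. The synopsis lists the same four.

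On the photon patients, the synopsis states: "Patients not willing or for any reason unsuitable to undergo proton treatment will be asked to participate in a follow-up assessment". Section 5.3 mentions only patients who decline the study but accept follow-up. Section 11 announces a descriptive toxicity analysis with a comparison between proton patients and a photon control group, and says no more about who belongs to that group.

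**The concern.** An exclusion that depends on how well protons planned is tied to the question the study asks. If patients whose proton plan was the worse one leave the study, what remains are patients for whom protons were at least as good on paper. A statement that proton therapy is feasible would then not show how often protons were set aside at planning.

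The same patients reappear on the other side. If they enter the photon comparator without being identified, a proton-photon difference in cardiac or pulmonary toxicity would partly reflect why each photon patient was in that group. A patient moved because of the plan comparison was selected on anatomy and dose distribution; a patient who declined protons need not have been. Pooled reporting would hide the distinction.

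**Working it through.** The protocol has no figure on this point to reproduce, so the check sets the sections side by side.

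1. **Is the criterion defined?** Only Sections 8.0 and 8.1 speak of a superior photon plan, and neither gives a measure, a threshold or an assessor. Table 2 ranks objectives and constraints for a plan, and Table 3 sets robustness tolerances. Neither is stated as a rule for comparing a proton plan with a photon plan. Table 2 sets no limit for the heart or the left anterior descending artery. Two plans could both satisfy Table 2 and the question of which is superior would stay open.

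2. **Is it an eligibility criterion?** It is in neither Section 6.2, nor Section 6.3, nor the synopsis list. Tumour motion, which is also found at planning imaging, is listed. So this protocol does place planning-stage exclusions in those lists, and this one is not there.

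3. **When can it take effect?** Section 5.9 makes registration depend on the eligibility criteria and consent. Plan superiority is neither. The pre-study list in Section 7.1 and Table 1 contain no plan comparison. Section 9.1 dates enrolment from signed consent. Nothing therefore prevents the exclusion from falling after enrolment, although nothing shows that it does.

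4. **What happens to the proton study?** Section 5.8 counts 40 evaluable patients who completed treatment according to the protocol, and Section 11 counts 40 included. A patient excluded under Section 8.0 is no longer in the study and so is not among the patients on whom a feasibility statement would rest.

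5. **What happens to the comparator?** The synopsis sends patients unsuitable for protons, whatever the reason, to photon follow-up. Section 8.0 sends the superior-plan patients to the photon cohort. Section 11 uses a photon control group, and no other photon group is described. That the two groups are the same is an inference, but it is the natural one.

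6. **How large is the effect?** Write *f* for the share of the photon group that came from the plan comparison, and *d* for the difference in toxicity rate between those patients and the refusers. The pooled photon rate is (1 − *f*) × refusers' rate + *f* × (refusers' rate + *d*) = refusers' rate + *f* × *d*. The protocol gives neither *f* nor *d*, nor the sign of *d*. For feasibility, the share is the number starting protons divided by the number planned for protons. The protocol gives only the 40, not the number planned. No size can be calculated.

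**The case against.** Several points on the other side stand.

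- **No feasibility proportion is planned.** Feasibility is in the overall aim but not among the primary or secondary objectives, and the background in Section 3.0 links the word to toxicity. A reader might infer that the study will report 40 of 40 patients as feasible and that this is biased by a calculable amount. The protocol proposes no such count, and every number of transfers would be assumed. What stands is that the aim is stated and the rule removes patients who bear on it.
- **The photon-group descriptions are largely compatible.** A reader might see a contradiction between the synopsis, Section 5.3 and Section 8.0. The synopsis wording is broad enough to cover all of them, and Section 5.3 says what refusers receive without claiming to list the whole cohort. What stands is that Section 11 does not define its control group.
- **Exclusion after registration is possible, not shown.** Section 8.0 opens by requiring that included patients can receive the prescribed dose within organ limits, which makes an acceptable plan a condition of inclusion. But acceptable is not the same as better than the photon plan, so the timing of the superiority judgement stays open.
- **Motion is already covered.** Section 8.6 says "If tumour motion exceeds 0.5 cm proton treatment will not be given and patient will receive the photon backup plan instead", and a reader might infer that these patients are unaccounted for. Section 6.3 already lists motion as an exclusion, so this is not part of the finding.
- **Other documents may help.** The photon cohort protocol named in Section 8.0 and the planning manual named in Section 8.5 are not shown and might define the cohort or the comparison. The analysis plan, also not shown, may set denominators. It cannot recover transfers that were never logged, and an exclusion rule belongs in the protocol's eligibility section.
- **The comparison is already non-randomized and descriptive.** That is disclosed. It does not tell the reader that some photon patients were placed there by the plan comparison.

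**Conclusion.** The concern holds in a limited form. The protocol contains an exclusion that is undefined, missing from its eligibility lists and not placed in time relative to registration. Following it removes patients for whom protons planned worse from the proton study and, on the natural reading of the synopsis, Section 8.0 and Section 11 together, pools them with refusers in the toxicity comparison.

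The conclusion rests on one inference, that the photon cohort is the photon control group, and on the possibility, not the demonstration, of exclusion after enrolment. The number of patients affected and the size and direction of any bias cannot be derived from the protocol. If such transfers are rare the effect is small, but without a log nobody could tell.

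**What to change.** 1. Log every consented patient planned for protons. Report how many started and how many completed protons, with exact 95% confidence intervals. Keep patients moved for a superior photon plan in that denominator, with the reason recorded.
2. List the plan-superiority exclusion in Section 6.3 with the sponsor's own criterion, written in advance, and its timing relative to registration. Reconcile it with Sections 8.0 and 8.1.
3. Define the photon control group in Section 11. Report photon patients by reason for being there (refusal versus superior photon plan or other unsuitability), and state that the comparison is not causal.

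The cost is wording in Sections 6.3, 8.0, 8.1 and 11 and a screening and transfer log. No new assessments are needed, because Section 8.0 already has these patients followed. The downsides are a possibly less favourable feasibility figure and small subgroups among the photon patients. No planning or dose rule is proposed here; what counts as a superior plan is for the sponsor to write down.
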